9.3.3. Administration

Subjects will be randomized (1:1) to receive either:

1. Arm A – ipilimumab 3 mg/kg i.v. at Weeks 1, 4, 7, and 10
or
2. Arm B – IMO-2125, 8 mg intratumorally at Weeks 1, 2, 3, 5, 8, 11, 16, 20, and 24 in combination with ipilimumab 3 mg/kg i.v. at Weeks 2, 5, 8, and 11

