## **7 GENERAL CONSIDERATIONS**

Analysis datasets will be created according to Clinical Data Interchange Standards Consortium (CDISC) standards, and data will be displayed according to reporting standards in this SAP and TLF formats.

SAS Version 9.4 or higher will be used to perform all data analyses and to generate tables, listings, and figures (TLFs).

All data collected in the database will be presented in data listings.

Idera Pharmaceuticals, Inc.  
Statistical Analysis Plan  
Protocol Number: 2125-MEL-301

---

For each subject, data up to the time of study completion, lost to follow-up, or withdrawal from study will be included in the appropriate analysis sets defined in [Section 6](#).

Continuous variables will be summarized in terms of the number of observations, mean, standard deviation, median, minimum, and maximum. Other descriptive statistics (e.g., quartiles, coefficient of variation) may be reported when appropriate. Categorical variables will be summarized using frequency counts and percentages. Analyses that use other descriptive statistics will be specified in the applicable SAP section.

Summaries will order displays by ipilimumab with IMO-2125 first, followed by the ipilimumab alone arm. Unless otherwise stated, summaries and figures will be reported by study arm. Summary statistics of central tendency will use one more decimal place than the collected data. Summary statistics of variability will use one more decimal place than the corresponding measure of central tendency. For example, the mean and median for age in years will be presented to one decimal place and the standard deviation of age will be reported to 2 decimal places. Percentages will be displayed to one decimal place, and proportions will be displayed to 4 decimal places. Durations for treatment exposure (weeks), adverse events (weeks), and response (months) will be displayed to 1 decimal place.

Planned visits will be used in all tables and figures that are by visit. Generally, only planned visits will be used in the summaries, statistical analyses, and calculations of any derived parameters; unscheduled visits will be included in the listings. However, both unscheduled and scheduled visits will be included in the determination of the worst-case (highest and/or lowest) post-baseline shifts for laboratory results, vital signs, and ECG.

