## **11.6 ADVERSE EVENTS OF SPECIAL INTEREST**

Systemic injection and infusion reaction such as cytokine release syndrome (CRS), anaphylactic and anaphylactoid reactions are deemed to be adverse events of special interest

Idera Pharmaceuticals, Inc.  
 Statistical Analysis Plan  
 Protocol Number: 2125-MEL-301

(AESIs). From communication with U.S. Food and Drug Administration (FDA) on 11 September 2020, the agency agreed with the Sponsor regarding the use of the American Society for Transplantation and Cellular Therapy (ASTCT) Consensus (Lee, 2019) for assessment of CRS events, and FDA’s guidance for the industry for immunogenicity assessment for evaluation of anaphylactic events. FDA recommended to assess any fever (not attributable to any other cause), hypotension and hypoxia, and to include related organ toxicities associated with CRS with severity graded according to CTCAE 4.03. FDA also recommended to include definitions of CRS, anaphylaxis, and hypersensitivity based on clinical diagnostic criteria and to provide an analysis based on the clinical criteria to distinguish CRS from anaphylaxis and hypersensitivity by presenting data on the nature, onset, frequency and severity, information about dose modifications and any evidence of recurrence with dose reduction or after drug withdrawal.

The Sponsor has used the following nine MedDRA LLTs for the initial database search for AESIs reported within 14 days after any tilso injections: anaphylaxis, cytokine release syndrome, infusion related reaction, injection site allergic reaction, injection related reaction, allergic reaction, anaphylactic reaction, anaphylactoid reaction, or systemic inflammatory response syndrome. A listing of AEs corresponding to these LLTs was generated to be used for evaluation against the ASTCT definition for CRS as well as the FDA guidance document on anaphylactic reaction which are provided below as a reference:

AE Term	Definition
CRS	A supraphysiologic response following any immune therapy that results in the activation or engagement of endogenous or infused T cells and/or other immune effector cells. A qualified CRS event will include fever along with hypotension and/or hypoxia.
Fever	A disorder characterized by elevation of the body’s temperature above the upper limit of normal, and a temperature of 38.0 °C is considered grade 1 fever.
Hypotension	A disorder characterized by a blood pressure that is below the normal expected for an individual in a given environment.

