Hypoxia	An Oxygen saturation (SaO 2 ) <94% or an individual requiring supplemental oxygen to correct a deficit in oxygenation is considered to have hypoxia. Oxygen provided only as a comfort measure should not be used.
Anaphylactic reaction	Anaphylaxis is a serious, acute allergic reaction without a particular immunologic mechanism and based on the following clinical features: 
 
1. Acute onset of an illness (minutes to several hours) with involvement of the skin, mucosal tissue, or both, and at least one of the following:               
 
• Hypoxia
 
• Hypotension
 
 
 
2. Two or more of the following that occur rapidly after exposure to Tilsotolimod (minutes to several hours):               
 
• Involvement of the skin-mucosal tissue
 
 
 

Idera Pharmaceuticals, Inc.  
 Statistical Analysis Plan  
 Protocol Number: 2125-MEL-301

AE Term	Definition
	
 
• Hypoxia
 
• Hypotension
 
• Persistent gastrointestinal symptoms
 

	
 
3. Hypotension after exposure to Tilsotolimod when prior systemic reactions with Tilsotolimod has occurred (minutes to several hours)
 

In order to perform a more comprehensive assessment of the AESIs, a search of all TEAEs which are coded under any of the following MedDRA SOC and started within 14 days after any tilsotolimod injections will also be conducted:

- General disorders and administration site condition
- Respiratory and mediastinal disorders vascular disorders
- Immune system disorders (see [Table 2](#) in Section 11.5)

The AEs identified will be reviewed and classified by the Sponsor as CRS, anaphylactic reaction or hypersensitivity reaction. The classification will be imported into the analysis dataset for summaries.

Significant AESIs will be summarized, that include Grade 3 and above systemic injection and infusion reactions.

Based on the strategy and definitions stated above, these AEs included under each event type will be determined based on a programmatic search of the AE datasets using the specified LLT in conjunction of a medical review of the AEs identified. The incidence of the AESIs under each event type will be summarized by MedDRA preferred term.

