Analyses of time to the first onset of the AESIs will be analyzed using the Kaplan-Meier product-limit method to estimate the quartiles and corresponding 95% confidence intervals for time to onset of each event. For this analysis, subjects who completed or prematurely terminated the study with the specified event will have the time to onset censored at the time of their completion or termination.

A listing of subjects who were identified to have experienced AESIs will be presented with onset, frequency and severity, information about dose modifications and any evidence of recurrence with dose reduction or after drug withdrawal.

Subject ID	PT	Sponsor assessed category	Grade	SAE	Time to Onset	Frequency	Recurrence after dose modification	Recurrence after drug withdrawal	Related Organ Toxicities and grades	Outcome
------------	----	---------------------------	-------	-----	---------------	-----------	------------------------------------	----------------------------------	-------------------------------------	---------

Abbreviation: PT = Preferred Term.

The following summaries will be provided:

- Significant Treatment-Emergent Adverse Events of Interest by Preferred Term

Idera Pharmaceuticals, Inc.  
Statistical Analysis Plan  
Protocol Number: 2125-MEL-301

---

- Time to Onset of Significant Treatment-Emergent Adverse Events of Interest

The following listing will be provided:

- Significant Treatment-Emergent Adverse Events of Interest

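### The AESI searches are tied to tilsotolimod injections alone, so the ipilimumab-only arm cannot contribute events to them, and the time-to-onset rule as printed censors subjects who had the event

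*SAP*

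**What the plan says.** SAP 11.6 sets the scope: "Systemic injection and infusion reaction such as cytokine release syndrome (CRS), anaphylactic and anaphylactoid reactions are deemed to be adverse events of special interest". Infusion reactions are therefore in scope as well as injection reactions, and the nine lower-level terms listed for the search include infusion related reaction and allergic reaction.

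Two searches follow. The nine terms were used "for the initial database search for AESIs reported within 14 days after any tilso injections". The wider search by system organ class takes treatment-emergent events that "started within 14 days after any tilsotolimod injections". No window after ipilimumab is given for either. Case selection for the summaries is then described: "Based on the strategy and definitions stated above, these AEs included under each event type will be determined based on a programmatic search". Of the three anaphylaxis criteria in the same section, the second and third refer to exposure to tilsotolimod; the first names no drug.

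On display, SAP 7 says: "Unless otherwise stated, summaries and figures will be reported by study arm". Section 11.6 states no exception. Section 11.7, on adverse events by injection type, does limit itself to the combination arm. The AESI outputs in SAP 16.2 (Tables 14.3.7.1 and 14.3.7.2) are titled for the Safety Set.

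For time to first onset, 11.6 says that "subjects who completed or prematurely terminated the study with the specified event will have the time to onset censored" when they complete or leave.

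**The concern.** An AESI table by arm is read as a comparison: how many more such reactions occur when IMO-2125 is added to ipilimumab. That needs the same case-finding in both arms. Here entry to the search depends on having received the experimental drug, so a control-arm zero would reflect the search and not the patients. The asymmetry runs one way: a reaction to ipilimumab can be counted in Arm B and cannot be counted in Arm A. SAP 11.6 records regulatory advice on how these events should be defined and presented, so the tables are likely to be read closely.

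The onset rule is a separate matter. A Kaplan-Meier analysis of time to first event should count first events and censor subjects who never had one. As printed, the rule censors those who had the event and says nothing about those who did not.

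**Working it through.** The plan states no figure on this point, so there is nothing to reproduce. The check lays the search windows over the dosing schedule.

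**Inputs**
- Arm A (Protocol 9.3.3): "Arm A – ipilimumab 3 mg/kg i.v. at Weeks 1, 4, 7, and 10". No IMO-2125, and no cross-over (Protocol 9.3.3.1).
- Arm B (Protocol 9.3.3): IMO-2125 at Weeks 1, 2, 3, 5, 8, 11, 16, 20 and 24; ipilimumab at Weeks 2, 5, 8 and 11.
- Tilsotolimod is taken to be IMO-2125. The SAP does not define the name, but 11.5 uses it alongside ipilimumab for the two study drugs.
- Week w starts on day 7(w − 1) + 1. A window runs from the dosing day to day +14, which is 15 days.

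**Window anchored to tilsotolimod, as written**
- Arm B injection days: 1, 8, 15, 29, 50, 71, 106, 134, 162. The first four windows join into days 1–43 (43 days). The other five are separate: 5 × 15 = 75. Total 43 + 75 = 118 days.
- Arm B ipilimumab days: 8, 29, 50, 71. All four are injection days, so 4 of 4 are covered.
- Arm A has no injection day: 0 days searchable, 0 of 4 infusions covered.

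**Window anchored to any study drug**
- Arm A ipilimumab days: 1, 22, 43, 64. Four separate windows give 4 × 15 = 60 days, with 4 of 4 infusions covered.
- Arm B is unchanged at 118 days, because each ipilimumab day is already an injection day.
- Counting only the windows after ipilimumab gives 4 × 15 = 60 days in each arm (Arm B: days 8–22, 29–43, 50–64, 71–85).

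**What a zero could hide.** The documents give no rate of such reactions on ipilimumab alone. Assume 1% to 10%, and take 227 per arm (454/2, planned randomised; the Safety Set size is not given). Then 0.01 × 227 ≈ 2 to 0.10 × 227 ≈ 23 Arm A subjects would have a reaction, and the searches would return none in every case.

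**Onset rule.** Assume 227 subjects, 30% with an event (68), onsets spread evenly over days 1–168, and everyone off study by the analysis.
- Censoring those without the event: 68 events; the curve ends at 1 − 68/227 = 0.70, and one simulated data set gave a first quartile of about 141 days.
- Literal rule: 0 events, the curve stays at 1.0, and no quartile can be estimated.

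Study completion is defined as death (Protocol 8.3.3), so the literal rule reaches every AESI subject who has died or withdrawn.

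**The case against.** **The Arm A column is inferred.** Mock displays are in separate documents (SAP 3), and 11.6 can be read as a description of tilsotolimod reactions only. The recorded regulatory advice asks for nature, onset, frequency and severity, not for a comparison between arms. This stands as a limit: a reader might infer that the table will certainly show 0 of 227 in Arm A, and the documents do not go that far. The column follows from a general default, and 227 is the planned number randomised, not the number dosed. If one arm was intended, however, 11.6 should say so, as 11.7 does.

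**The case-selection sentence does not repeat the window.** True, and it adds a medical review; the first search is also called initial. But the sentence opens by relying on the strategy already stated, so it does not admit Arm A events.

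**Other tables show Arm A reactions.** A reader might infer that control-arm reactions vanish from the report and that the excess on IMO-2125 cannot be judged at all. The documents do not support that. SAP 11.2 to 11.4 tabulate events by preferred term in both arms: all treatment-emergent, Grade 3 or above, treatment-related, serious, and leading to discontinuation. What Arm A lacks is the sponsor's classification, which is the purpose of 11.6.

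**An any-dose window is not automatically like for like.** Correct: 118 against 60 days would mix drug effect with search time unless this is handled.

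**The censoring wording is a slip.** Very likely, since the same paragraph asks for quartiles of time to first onset. It would be too strong to predict that the analysis will lose its events; a programmer may well implement the evident intention. The sentence still specifies a planned table.

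**Conclusion.** The point holds as an asymmetry in case-finding. Arm A cannot contribute events found by the two AESI searches, while all four Arm B ipilimumab infusions fall inside them (118 searchable days against 0). Any Arm A column produced under the by-arm default would therefore be zero as an artefact. The onset rule is wrong as printed and probably a one-word error.

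This rests on tilsotolimod being IMO-2125, on nominal dosing days with full treatment, and on the by-arm default applying to 11.6. The rates of 1% to 10% and 30% are assumptions for illustration only. The consequence is confined to descriptive safety output. ORR, OS and the alpha allocation are not touched. It should be corrected before the AESI tables are produced.

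**What to change.** Choose one scope and write it into SAP 11.6.

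1. **Both arms.** Anchor both 14-day windows, and the exposure wording in anaphylaxis criteria 2 and 3, to any dose of either study drug. Re-run the search and the sponsor's classification in both arms. Section 11.5 already reviews immune-related events relative to dosing of either drug, so there is a model to follow. State the unequal search time and account for it, for example by also reporting the ipilimumab dosing period alone, where the windows after infusions total 60 days in each arm.
2. **Combination arm only.** Say so in 11.6, as 11.7 does, and show no Arm A column.

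In either case, change *with* to *without* in the onset censoring rule, so that first onsets are events and subjects without the event are censored.

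Option 2 and the censoring correction need SAP wording only. Option 1 also needs new search output and medical review of the Arm A events, because the term listing has already been generated under the tilsotolimod window. Adverse events are already recorded in both arms, so no new data collection is needed.

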### **11.7 SUBGROUP ANALYSIS FOR ADVERSE EVENTS**

Adverse events will be further examined by Injection Type as reclassified by the Sponsor in [Section 11.1](#) [Visceral (Organ), Deep, and Superficial]. Any summaries by injection type will be performed for the combination treatment arm only.

The following tables will be provided for the AE subgroup analysis:

- Treatment-Emergent Adverse Events by Preferred Term and Injection Type
- Grade 3 or Above Treatment-Emergent Adverse Events by Preferred Term and Injection Type
- Serious Treatment-Emergent Adverse Events by Preferred Term and Injection Type
- Deaths by Injection Type

### **11.8 CLINICAL LABORATORY EVALUATIONS**

The laboratory tests in [Section 12.2](#) of the protocol, Laboratory Assessments, will be summarized as described in this section.

Idera Pharmaceuticals, Inc.  
 Statistical Analysis Plan  
 Protocol Number: 2125-MEL-301

Category	Analyte
Hematology	CBC: white blood cell (WBC), red blood cell (RBC), hemoglobin, hematocrit, platelet count, mean corpuscular hemoglobin (MCH), mean corpuscular hemoglobin concentration (MCHC), mean corpuscular volume (MCV) Differential WBC count: neutrophils, monocytes, lymphocytes, eosinophils, basophils, atypical lymphocytes
Coagulation	prothrombin time (PT), activated partial thromboplastin (aPTT), international normalized ratio (INR)
Complement	CH50, C3, C4
Clinical Chemistry Panel	Renal: Serum sodium, potassium, chloride, carbon dioxide (CO 2 ), calcium, phosphate, creatinine, blood urea nitrogen, uric acid
	Endocrine: serum glucose, free thyroxine (free T 4 ), total or free triiodothyronine (total or free T 3 ), thyroid stimulating hormone (TSH)
	Liver: serum alanine aminotransferase (ALT), aspartate aminotransferase (AST), lactate dehydrogenase (LDH), alkaline phosphatase, albumin, total protein, total bilirubin
	Lipids: Serum cholesterol, triglycerides
Urinalysis	Dipstick testing (urinalysis and microscopy will be conducted only if dipstick results are abnormal)

Laboratory data will be presented in International System of Units (SI) and in the order presented in the protocol. Laboratory grades will be reported using the CTCAE v4.03 (see [Appendix Section 16.5](#)); ungraded laboratory assessments will be reported using normal ranges.

Laboratory tests that are graded for both low and high abnormal values will have both values summarized separately with directions (hyper- or hypo-) labeled accordingly.

Separate summary tables of the observed and change from baseline values for hematology, chemistry, coagulation, and complement laboratory tests will be produced.

Definition of the baseline assessment is in [Section 8.2.5](#).

The denominator in percentage calculations at each scheduled visit will be based on the number of subjects with a non-missing value at each visit.

Idera Pharmaceuticals, Inc.  
Statistical Analysis Plan  
Protocol Number: 2125-MEL-301

---

Hematology and chemistry laboratory tests will be summarized using shift tables by treatment arm. Subjects must have a baseline and at least one non-missing post-baseline assessment to be included in the shift analysis.

Summaries of shifts from baseline will be provided for hematology and chemistry laboratory tests that are graded by CTCAE v4.03 ([Appendix Section 16.5](#)). This shift table will include a worst-case (defined as the highest CTCAE grade) post-baseline summary that includes data from both scheduled and unscheduled visits. Categories based on value ranges for CTCAE grades will be shown for baseline and worst case post-baseline, with the number and percentage of subjects in each.

Summaries of shifts from baseline with respect to the normal range will be provided for the following laboratory parameters: WBC, RBC, hematocrit, platelet count, neutrophils, lymphocytes, total bilirubin, creatinine, LDH, ALT, AST, and TSH. This shift table will include both shift to lowest and shift to highest post-baseline with respect to the normal range. All data from both scheduled and unscheduled visits will be considered for the shifts. Categories of normal range, below the normal range, and above the normal range will be shown for baseline, the highest and the lowest post-baseline, with the number and percentage of subjects in each. A figure showing the mean, median, quartiles, range, and outliers beyond the interquartile range (boxplot) for each treatment arm at each scheduled visit will be produced for hematology and chemistry parameters. It will have the nominal visit assessment week on the horizontal axis and the parameter value on the vertical axis. The number of subjects assessed in each treatment arm will be displayed below each visit.

A paneled scatterplot of the ratio of maximum total liver function tests to ULN versus baseline liver function tests to ULN will be produced by treatment arm. The liver function tests included in the plot are ALT, AST, total bilirubin, and alkaline phosphatase.

Listing of all laboratory values will be provided with the CTCAE v4.03 grade (if applicable) and laboratory values LLN and ULN will be flagged.

Summaries to be produced are:

- Summary of Change from Baseline in Hematology
- Summary of Change from Baseline in Chemistry
- Summary of Change from Baseline in Coagulation
- Summary of Change from Baseline in Complement
- CTCAE Shifts from Baseline Grade in Hematology
- CTCAE Shifts from Baseline Grade in Chemistry
- Shifts from Baseline Relative to the Normal Range in Selected Laboratory Tests

Idera Pharmaceuticals, Inc.  
Statistical Analysis Plan  
Protocol Number: 2125-MEL-301

---

Figures to be produced are:

- Boxplot for Hematology
- Boxplot for Chemistry
- Liver Function Tests Maximum Values to ULN on Study vs Baseline to ULN

Listings to be produced are:

- Hematology
- Chemistry
- Coagulation
- Complement
- Dipstick Test and Urinalysis

## **11.9 OTHER SAFETY MEASURES**

The denominator in percentage calculations at each scheduled visit will be based on the number of subjects with non-missing values at each visit.

### **11.9.1 Vital Signs and Weight**

Blood pressure values will be categorized into the ranges as listed in [Section 8.3.3](#).

Summary of shifts in blood pressure from baseline will be provided. This shift table will include a summary of the highest and the lowest post-baseline that includes data from both scheduled and unscheduled visits. Categories will be shown for baseline, the highest and the lowest post-baseline, with the number and percentage of subjects in each. Subjects must have a baseline and at least one non-missing post-baseline assessment to be included in the shift analysis.

Summary of shifts in heart rate and temperature from baseline to lowest and highest post-baseline value will be provided. The actual values will be categorized into the ranges as listed in [Section 8.3.3](#). Number and percentage of subjects in each of the categories will be presented for the lowest and highest post-baseline.

Summaries to be produced are:

- Shifts in Blood Pressure from Baseline to Lowest and Highest Post-Baseline
- Shifts in Heart Rate and Temperature from Baseline to Lowest and Highest Post-Baseline

The listing to be produced is:

Idera Pharmaceuticals, Inc.  
Statistical Analysis Plan  
Protocol Number: 2125-MEL-301

---

- Vital Signs (including out of range indicator)

